### 1.4 Objectives

**Primary Objective:** To investigate the effect of crisaborole (Eucrisa™) treatment on patient-reported itch and pain in patients with mild to moderate atopic dermatitis compared to tacrolimus 0.03%.

- *Hypothesis:* We hypothesize that crisaborole (Eucrisa™) treatment will significantly decrease (i.e., score change  $\geq 5$ ) the severity of itch and pain over time and these changes will correlate with improvements Eczema Area and Severity Index (EASI) in atopic dermatitis. We further hypothesize that the improvement in these PROs will be greater in the crisaborole treated subjects compared to those receiving tacrolimus.
- *Primary Outcome Measures:* Change in PROMIS® Itch and PROMIS® Pain Interference measures after 12 weeks of treatment.

**Secondary Objective:** To investigate the effect of crisaborole (Eucrisa™) treatment on patient-reported quality of life, sleep, anxiety, and depression in patients with mild to moderate atopic dermatitis compared to tacrolimus 0.03%.

- *Hypothesis:* We hypothesize that crisaborole (Eucrisa™) treatment will improve quality of life and decrease (i.e., score change  $\geq 5$ ) the severity of one or more of the PROs (sleep, anxiety, or depression). These changes will correlate with improvements in atopic dermatitis (EASI). We also hypothesize that the improvement in these PROs will be greater in the crisaborole treated subjects compared to those receiving tacrolimus.
- *Secondary Outcome Measures:* Change in Children’s Dermatology Life Quality Index (CDLQI), PROMIS® Anxiety, PROMIS® Depression, and Children’s Sleep Habits Questionnaire (CSHQ) after 12 weeks of treatment.

**Tertiary Objective:** To elucidate the impact of crisaborole (Eucrisa™) treatment or tacrolimus 0.03% on caregiver burden.

- *Hypothesis:* We hypothesize that improvements in caregiver burden will correlate with improvements in atopic dermatitis (EASI), as well as decreased severity in PROs.
- *Tertiary Outcome Measures:* Change in Caregiver Burden Inventory and Family Dermatology Life Quality Index (FDLQI) after 12 weeks of treatment.

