#### **5.5. Blinding Methods**

This is an open-label study and is not blinded.

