## **6. CONCOMITANT AND DISALLOWED MEDICATIONS**

Systemic anti-inflammatory therapies for atopic dermatitis are allowed if the subject is taking a stable dose of the systemic anti-inflammatory medication for at least six week prior to enrollment. It must be anticipated that this stable dose would not change during their participation in this study, unless deemed medically necessary. Any changes in systemic medication dose due to flaring of atopic dermatitis or side effects will be documented on the *AD Flare Medication Form* and *AE Source Doc* (see page 19). These therapies are not usually used in children with atopic dermatitis of moderate or less severity. If a subject is newly prescribed systemic anti-inflammatory therapy during the course of the study due to worsening atopic dermatitis, the subject will be withdrawn from the study.

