## **7. SUBJECT WITHDRAWALS**

Subjects will be advised during the consent/assent process that they have the right to withdraw from the study at any time without prejudice or reason. Criteria for investigator-initiated subject withdrawal include: inability to make study visits, subject lost to follow-up, non-compliance to study procedures, or death. The reason for discontinuation will be recorded in the subject's medical records. The date of occurrence and reasons for any subject withdrawal will be recorded and documented on the **Withdrawal Form**. Subjects that withdraw from the study will be replaced with another subject.

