## **8. STOPPING PROCEDURES**

- Subjects will remain on study during an atopic dermatitis flare. Any extra medication prescribed to control the flare will be documented on the electronic AD Flare Medication Form. Subjects will continue all study procedures as described in the protocol. Subjects will continue to use their assigned study topical medication.
- Subject will be withdrawn from the study if systemic anti-inflammatory therapy is newly prescribed and required for control of their atopic dermatitis.

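### Withdrawn children are replaced and no later outcomes are sought, so by default the week-12 arm comparison rests on the children who stayed

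*Combined protocol and SAP*

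**What the plan says.** **Withdrawal and replacement.** Section 7: "Subjects that withdraw from the study will be replaced with another subject". The staff-initiated grounds are broad: "Criteria for investigator-initiated subject withdrawal include: inability to make study visits, subject lost to follow-up, non-compliance to study procedures, or death". Section 8 adds one tied to the disease: "Subject will be withdrawn from the study if systemic anti-inflammatory therapy is newly prescribed and required for control of their atopic dermatitis". Section 6 repeats this rule.

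**Outcomes after withdrawal.** Section 7 asks for a record: "The date of occurrence and reasons for any subject withdrawal will be recorded and documented on the" Withdrawal Form. Neither that section nor Section 8 says whether questionnaires or EASI are still sought. Section 5.3 (Call Log) foresees extra contact after missed or cancelled visits, but says nothing about a child already withdrawn.

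**Endpoint and analysis.** The primary outcome in Section 1.4 is "Change in PROMIS® Itch and PROMIS® Pain Interference measures after 12 weeks of treatment". Section 11.1 treats a child as evaluable once the week-6 assessment is done. Section 11.2 lists ANCOVA, correlation and regression for change from baseline to week 12, and longitudinal analyses for change over time. Its one sentence comparing the arms on itch and pain names two-tailed t-tests on the changes. No analysis set by allocated arm and no rule for a missing week-12 value is given.

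**Limiting text.** Section 8: "Subjects will remain on study during an atopic dermatitis flare". Section 6, on systemic treatments: "These therapies are not usually used in children with atopic dermatitis of moderate or less severity". Section 5.6 measures use of the ointment by tube weight. Section 5.3 records withdrawal and treatment for each pair and foresees a CONSORT diagram.

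**The concern.** Randomisation makes the arms comparable when all randomised children are compared. Here at least one route out, new systemic therapy for worsening dermatitis, depends on how the child is doing. Another, non-compliance, is decided by staff who know the treatment: "This is an open-label study and is not blinded". If such withdrawals are more common in one arm, that arm sheds its poorer responders and looks better than it is. A replacement child fills the place but tells us nothing about the child who left.

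A child withdrawn at week 8 shows the gap. That child is evaluable under Section 11.1, has no value for the primary outcome in Section 1.4, and has no stated place in the comparison in Section 11.2. A t-test on 12-week change drops the child by default.

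If outcome-related withdrawal is equal in both arms, with similar gaps, the arm difference is little affected. The within-arm improvement, which Section 1.4 also hypothesises, could still be overstated.

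**Working it through.** **The plan's own figure.** Section 11.1 gives 48 pairs for 40 evaluable with 20% loss. 40 x 1.2 = 48 reproduces it. (Dividing by 0.8 gives 50, and 48 x 0.8 = 38.4; the difference is small and is not the point here.) At 1:1, 48 is 24 randomised per arm. The 20% is an overall rate; the documents give none by arm.

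**Formula.** Let a share p of an arm withdraw, with a mean change g points worse than that of the children who stay. The mean of all children is then the stayers' mean plus p x g. A comparison of stayers therefore shifts the arm difference by (pA - pB) x g.

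**Inputs.** From Section 11.1: SD 10, 20 evaluable per arm, two-sided 0.05. Taking the SD as that of the change, SE = 10 x sqrt(2/20) = 3.16. The withdrawal shares and the gap of 5 to 10 points are assumptions. For scale, Section 5.3 calls a change of 5 points clinically important for Pain Interference.

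| Assumed withdrawal | Gap | Shift | Shift / SE | False-positive rate |
|---|---|---|---|---|
| 1 of 24 vs 0 | 5 | 5/24 = 0.21 | 0.07 | 5.05% |
| 1 of 24 vs 0 | 10 | 10/24 = 0.42 | 0.13 | 5.2% |
| 20% vs 5% | 5 | 0.15 x 5 = 0.75 | 0.24 | 5.6% |
| 20% vs 5% | 10 | 0.15 x 10 = 1.5 | 0.47 | 7.5% |

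The last column is the two-sided rejection rate with no true difference, from the noncentral t distribution on 38 degrees of freedom.

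Children under 5 give no PROMIS scores (Section 5.1). If ages were spread evenly over 2 to 15, 11/14 x 20 = 15.7, about 16 per arm, would contribute. Then SE = 10 x sqrt(2/16) = 3.54, and the 20% vs 5% rows become 0.21 and 0.42 SE, with rates of 5.5% and 7.0%.

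**What baseline adjustment gains.** With correlation r between baseline and week 12, the SD of change is 10 x sqrt(2(1 - r)) and the adjusted SD is 10 x sqrt(1 - r^2). At 20 per arm:
- r = 0.5: SDs 10.0 and 8.66; SE falls from 3.16 to 2.74.
- r = 0.7: SDs 7.75 and 7.14; SE falls from 2.45 to 2.26.

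This gain holds even if nobody withdraws.

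**Why a model using week 6 is not enough.** A large simulation used no true difference, SD 10, equal correlation between visits, and removal of the 20% vs 5% of children who worsened most between weeks 6 and 12. Regression on baseline and week 6 stood in for the repeated-measures model. With no week-12 values recovered, the arm difference was off by:
- r = 0.5: 1.21 points for completers, 1.93 for the model.
- r = 0.7: 0.93 points for completers, 1.55 for the model.

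Children who worsen late tend to have good week-6 scores, so the model predicts too well for them. With half of the missing week-12 values recovered, the model's error falls to 0.73 (r = 0.5) or 0.59 (r = 0.7); with 80% recovered, to 0.25 or 0.21. If withdrawal follows the observed week-6 change instead, the model is unbiased. These runs show the order of the methods, not the likely size in this trial.

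**The case against.** The case for leaving the plan alone has real weight.

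- **The outcome-related route is narrow.** Flaring children stay on study and systemic therapy is unusual at this severity. Tube weight makes non-compliance with treatment partly objective, although Section 7 refers to study procedures more widely. Contact after missed visits should reduce loss. All of this stands and is why the likely size is small.
- **ANCOVA is already listed.** The primary objective is comparative, so the ANCOVA in Section 11.2 may be meant for the arms. That is possible, but the text attaches it to change from baseline and gives the arm comparison to t-tests. If ANCOVA was intended, the SE gain is already in the plan; in either case that gain is not evidence of a withdrawal problem.
- **Continued collection reaches only some children.** Death and loss to follow-up leave no one to assess, and a family that withdraws consent must be left alone. The consent pages were not available, so what they allow after withdrawal could not be checked.

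A reader might infer that the plan forbids follow-up after withdrawal or discards the data of replaced children. It says neither. Replacement may simply be how the margin from 40 to 48 is used. The point is that the plan is silent, and that its default analysis drops children without a week-12 value.

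**Conclusion.** The point stands as a minor to moderate one. Followed as written, the plan gives a week-12 comparison of children who stayed, and replacement does not correct that. The gap lies in outcome collection and in the analysis rule, not in the withdrawal records.

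Under the assumed 5 to 10 point gap, the shift is 0.2 to 0.4 points for one extra withdrawal in 24 and 0.75 to 1.5 points for 20% against 5%. The second split is an illustration without support in the documents. Direction is unknown.

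A reader might infer a larger bias, for example by supposing that exactly the children with the worst total change leave. That implies withdrawn children 17.5 to 21.7 points worse than those retained at r = 0.5 (13.5 to 16.8 at r = 0.7), well beyond the 5 to 10 points used here and with no basis in the documents. A reader might also infer that one ointment will be favoured; no stated rate supports that.

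**What to change.** Leave treatment and all rules for stopping treatment as they are.

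1. **Sections 7 and 8 (the main step).** State that week-6 and week-12 questionnaires and EASI are still sought from every randomised child who can be contacted and whose consent or assent stands, including children later replaced. Telemedicine visits, already allowed in Section 5.1, can be used where needed.
2. **Section 11.2.** Make the between-arm comparison of week-12 itch and pain an ANCOVA adjusted for the baseline score, in place of t-tests on change. Include all randomised children eligible for the measure (age 5 or over for PROMIS), by allocated arm, with replaced children kept in. State how a child without a week-12 value is handled.
3. **Section 11.1.** Use evaluable for accrual counts only, and report withdrawals by arm and reason from the records already planned.
4. **Sensitivity analyses.** Report a repeated-measures model that uses week 6, with the caveat that without recovered week-12 values it can be more biased than completers if withdrawal follows worsening after week 6. Report also an analysis that excludes values after new systemic therapy.

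**Cost.** Some wording and a few more questionnaires. At the payments in Section 5.8 ($40 caregiver plus $10 child per follow-up visit), two visits for 8 withdrawn pairs (48 - 40) cost at most 8 x 2 x $50 = $800.

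**Downside.** Some week-12 values will reflect added systemic therapy. Section 1.3 reports a 7.0-point fall in Pain Interference in adults starting such treatment. If children responded similarly, one child in 24 would move an arm's mean by 7.0/24 = 0.3 points, and 20% of an arm by 0.20 x 7.0 = 1.4 points; hence the second sensitivity analysis. ANCOVA alone does not bring back children without a week-12 value, so step 1 matters most.

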## **8. STOPPING PROCEDURES**

- Subjects will remain on study during an atopic dermatitis flare. Any extra medication prescribed to control the flare will be documented on the electronic AD Flare Medication Form. Subjects will continue all study procedures as described in the protocol. Subjects will continue to use their assigned study topical medication.
- Subject will be withdrawn from the study if systemic anti-inflammatory therapy is newly prescribed and required for control of their atopic dermatitis.

## **9. SAFETY AND REPORTABLE EVENTS**

### **9.1. Adverse Event Monitoring**

This study does not involve interventional or clinical endpoints for individual patients. The treatment prescribed to patients in the study is part of standard care for mild to moderate atopic dermatitis in children and adolescents. Although the patients will receive one of two topical treatments for atopic dermatitis, the primary outcome of the study is not clinical response to treatment. Crisaborole and tacrolimus 0.03% ointments are both FDA-approved for atopic dermatitis and applied twice daily to affected areas of skin. Although this is an open-label, cross-sectional study, safety information may be identified during the course of data collection. Adverse event monitoring will be performed by phone at four different times during the study (i.e., Week 3, Week 6, Week 9, and Week 12). Any AEs will be documented on the AE Source Doc. Any safety information for an individual patient that is volunteered by a study subject during the course of this research must be reported as described below:

All adverse event, whether observed by the Investigator, elicited from, or volunteered by the subject, should be documented. Each adverse event will be recorded on the electronic AE Source Doc. This form will record the will include a brief description of the experience, the date of onset, the date of resolution, the duration and type of experience, the severity, contributing factors, and any actions taken. This description will be in the summary not during a subject's regularly scheduled clinic appointment.

**Adverse event (AE):** is any untoward medical occurrence in a subject administered study drug (active drug or placebo), and which does not necessarily have a causal relationship with this treatment. An adverse event can be any unfavorable and unintended sign (including abnormal laboratory test results), symptom, or disease temporally associated with the use of the study drug, whether or not considered related to the study drug. The relationship of each adverse event to the study drug (active drug or placebo) must be recorded as one of the choices on the scale described below.

**Attribution:** An assessment of the relationship between the adverse event and the protocol treatment, using the following categories.

ATTRIBUTION	DESCRIPTION
Unrelated	The AE is clearly NOT related to treatment.
Unlikely	The AE is doubtfully related to treatment.
Possible	The AE may be related to treatment.
Probable	The AE is likely related to treatment.
Definite	The AE is clearly related to treatment

**Hospitalization (or prolongation of hospitalization):** For AE reporting purposes, a hospitalization is defined as an inpatient hospital stay equal to or greater than 24 hours.

**Life Threatening Adverse Event:** Any AE that places the subject at immediate risk of death from the AE as it occurred.

**Serious Adverse Event (SAE):** Any adverse event occurring at any dose that results in **ANY** of the following outcomes:

- Death
- A life-threatening adverse event
- Inpatient hospitalization or prolongation of existing hospitalization (for  $\geq 24$  hours).

- A persistent or significant incapacity or substantial disruption of the ability to conduct normal life functions.
- A congenital anomaly/birth defect.
- Important Medical Events (IME) that may not result in death, be life threatening, or require hospitalization may be considered a serious when, based upon medical judgment, they may jeopardize the subject and may require medical or surgical intervention to prevent one of the outcomes listed in this definition.

## 9.2. Recording Adverse Events

Study personnel will assess adverse events by recording all voluntary complaints of the subject. Any side effects and adverse reactions will be noted on the AE Source Doc. Study personnel will check with the nurse and/or treating physician regarding any reported adverse reactions. All adverse events, whether observed by the Investigator, the treating physician, or volunteered by the subject, will be documented. Adverse events will be reported per the RSRB and CTO reporting requirements. Each adverse event will include a brief description of the experience, the date of onset, the severity of the event, the relationship to investigational intervention, and any action taken with respect to the study and intervention. Adverse event monitoring will occur at the start of topical treatment until completion of the study.

The relationship to the study drug and the severity of each adverse event (i.e., attribution) as judged by the investigator must also be recorded. An adverse event is any untoward medical occurrence in a patient administered study drug (active drug or placebo), and which does not necessarily have a causal relationship with this treatment. An adverse event can be any unfavorable and unintended sign (including abnormal laboratory test results), symptom, or disease temporally associated with the use of the study drug, whether or not considered related to the study drug. The relationship of each adverse event to the study drug (active drug or placebo) must be recorded as one of the choices on the scale below:

**DEFINITE**: Causal relationship is certain (e.g., the temporal relationship between drug exposure and the adverse event onset/course is reasonable; there is a clinically compatible response to de-challenge; other causes have been eliminated; and the event must be definitive pharmacologically or phenomenologically using a satisfactory re-challenge procedure, if necessary).

**PROBABLE**: High degree of certainty for causal relationship (e.g., the temporal relationship between drug exposure and the adverse event onset/course is reasonable; there is a clinically compatible response to de-challenge [re-challenge is not required]; and other causes have been eliminated or are unlikely).

**POSSIBLE**: Causal relationship is uncertain (e.g., the temporal relationship between drug exposure and the adverse event onset/course is reasonable or unknown; de-challenge/re-challenge information is either unknown or equivocal; and while other potential causes may or may not exist, a causal relationship to study drug does not appear probable).

**UNLIKELY**: Not reasonably related, although a causal relationship cannot be ruled out (e.g., while the temporal relationship between drug exposure and the adverse event onset/course

does not preclude causality, there is a clear alternate cause that is more likely to have caused the adverse event than the study drug).

**UNRELATED:** No possible relationship (e.g., the temporal relationship between drug exposure and the adverse event onset/course is unreasonable or incompatible, or a causal relationship to the drug is not plausible).

### **9.3. Reporting Serious Adverse Events**

Serious adverse events (SAEs), while a subject is enrolled in the study until the subject completes the study, will be reported in writing to the University RSRB as per their requirements. A serious event refers to any event in which the outcome results in any of the following: death, a life-threatening adverse drug experience, inpatient hospitalization or prolongation of existing hospitalization, a persistent or significant disability, incapacity, or a congenital anomaly/birth defect. Important medical events that may not result in death, be life-threatening, or require hospitalization, may be considered a serious adverse experience when, based upon appropriate medical judgment, they may jeopardize the subject and may require medical or surgical intervention to prevent one of the outcomes listed in this definition. Hospitalizations scheduled for an elective procedure or for treatment of a pre-existing condition that has not worsened during participation in the study, will not be considered serious adverse events. The onset date, resolution date, treatment, and outcome of each adverse event will be reported to the Research Subjects Review Board (RSRB) and to the Safety Coordinator using the MedWatch Form FDA 3500A-Mandatory Reporting. Unanticipated problems that involve risks to subjects or others (UPIRTSO) will be reported to RSRB.

**Pfizer:** Serious adverse events must be reported to Pfizer using the Pfizer-provided SAE form. The Pfizer SAE form will be faxed to [REDACTED] along with the MedWatch Form FDA 3500A-Mandatory Reporting and Pfizer Reportable Event Cover Sheet. SAEs should be reported to Pfizer immediately upon awareness, if the SAE is fatal or life-threatening (i.e., causes an immediate risk of death) —regardless of the extent of available information. Alternatively, SAEs should be reported within 24 hours of first awareness of the SAE, if the SAE is not fatal or life threatening. Non-serious adverse events observed in the trial *are not* reported to Pfizer.

**IRB:** As described above, on-study adverse reactions are reported to the University of Rochester Research Subjects Review Board (RSRB). Modifications to the protocol will be reviewed by RSRB before implementation. The RSRB also provides initial and continuing review of study conduct and consent.

**Research staff (i.e., PI, Co-investigators, or study coordinator):** Will also conduct continuous review of data and subject safety. The review will include for each treatment arm/dose level: the number of subjects, adverse reactions, and responses observed. The Investigator will submit summaries of this data to the Data Safety Monitoring Committee for review as required in the study's protocol review committee approval letter.

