### **11.3. Data Safety Monitoring Plan**

[REDACTED]. Approval of protocol, informed consent procedures, and recruitment will be obtained from the IRB. Because this study's procedures pose relatively low risk to subjects, monthly data and procedural reviews by the Clinical Monitor and Investigator in consultation with study personnel will be sufficient to identify and ameliorate any potential safety issues. Any safety concerns about the clinical protocol will be brought to the immediate attention of the Principal Investigator and Co-Principal Investigator. Study personnel will follow aforementioned reporting procedures for adverse event reporting, including any serious adverse events. Protocol deviations and quality issues will be recorded and reported to the IRB per local policies. Remedial and/or corrective action to prevent reoccurrence of protocol deviations or quality issues will be instituted as necessary.

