[REDACTED] and assigned study personnel using their University-specific login and password. All completed paper questionnaires will be stored in study folders in a locked cabinet in [REDACTED]. All paper questionnaire data will be electronically entered into the RedCap database using a electronic data collection form. All forms will be coded by Subject Pair ID and Initials. The coding key will be stored electronically on the password-protected, encrypted, desktop computer connected to the University's secure server in [REDACTED]. The coding key will be stored for the length of the study and then permanently deleted at the completion of the study.

**Data Monitoring:** The REDCap database will be audited monthly to ensure accurate data collection and entry. No subject identifying data will be used. All of the written material will be kept confidential, locked in the private office of the principal investigator and identified only by Subject Pair ID. At completion of the whole study (including final analyses), all paper forms will be destroyed.

**Data Storage and Confidentiality:** All data for this study is electronic and will be stored in the secure, study-specific, password-protected REDCap database or on the secure [REDACTED]

[REDACTED] All paper documents will be stored in a locked file cabinet in [REDACTED].

Study personnel will have access to the study data. Statistical analyses will be performed on de-identified dataset containing Subject Pair IDs.

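### Section 9.3 has study staff review responses by treatment arm continuously, which no planned decision uses and which adds a modest, avoidable source of bias to an open-label trial

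*Combined protocol and SAP*

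**What the plan says.** Under its paragraph on research staff, section 9.3 names the PI, co-investigators or study coordinator and says that they "Will also conduct continuous review of data and subject safety". The content is then specified: "The review will include for each treatment arm/dose level: the number of subjects, adverse reactions, and responses observed". The results go onward: "The Investigator will submit summaries of this data to the Data Safety Monitoring Committee for review".

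Four other sections bear on the point:
- Section 5.5 states that the study is open-label.
- Section 7 lets the investigator withdraw a child for reasons that include non-compliance with study procedures, and adds that "Subjects that withdraw from the study will be replaced with another subject".
- Section 5.3 (AD Flare Medication Form) leaves flare management to the treating dermatologist's discretion.
- Section 12 says that "Study personnel will have access to the study data", with no exception for outcome data grouped by arm.

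**The concern.** Reviewing adverse events by arm is ordinary safety oversight. Reviewing responses by arm is a running efficacy comparison, here given to the people who conduct the trial. In an unblinded study, knowing which treatment is ahead can influence how firmly a poorly complying child is pursued or withdrawn, how readily extra flare medication is given, how families are encouraged, and how a borderline sign is graded. Sections 1.2 and 1.4 also state in advance that crisaborole is expected to do better, so early figures would be read against a known expectation. At stake is the credibility of the between-arm comparison of itch and pain interference, and of EASI and ISGA.

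**Working it through.** The point rests on no figure in the plan, so the check sets the sections side by side.

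1. **Does the instruction cover efficacy data?** The sentence in section 9.3 lists three items: numbers of subjects, adverse reactions, and responses. Responses stand apart from adverse reactions, so they are not a second name for them. The term is not defined. Section 9.1 says that the primary outcome is not clinical response, so it may mean EASI or ISGA, the PROs, or both. On any of these readings it is outcome data by arm.

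2. **Does a planned decision use it?** Section 8 concerns stopping for individual children only. Sections 11.1 and 11.2 describe tests at the two-sided 0.05 level on change from baseline to week 12, with no interim look, boundary or alpha adjustment. Section 11.3 directs its monthly review to safety issues. No decision in the plan calls for responses by arm during the trial.

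3. **Does anything keep the data from study staff?** No. Section 12 gives study personnel access. The Data Safety Monitoring Committee does not act as a barrier, because section 9.3 has the Investigator prepare the summaries that it receives.

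4. **Which decisions could the knowledge reach?** The clearest link is withdrawal. The investigator is both a reviewer (section 9.3) and the person who may withdraw a child (section 7). Non-compliance has no definition there, and the tube weighing in section 5.6 has no threshold. Flare treatment is discretionary (section 5.3). EASI and ISGA are scored by trained study personnel, and no masked assessor is named (section 5.1).

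5. **How does it reach the primary outcomes?** Only indirectly. Children aged 5 or older complete PROMIS Itch and Pain Interference on an iPad, with a parent's help if needed (sections 5.1 and 5.3). Staff do not score them. Itch is converted to a score only at analysis. Section 5.3 contrasts this with the other PROMIS measures, which implies that Pain Interference scores are available as the trial runs. The route is through encouragement, flare treatment, withdrawal and replacement.

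6. **What does it add to open-label conduct?** Staff dispense the assigned tube and log the treatment (sections 5.1 and 5.3), so they know each child's arm and course. The addition is the arm-level comparison. With 40 evaluable pairs (48 accrued), staff might form a rough impression of it unaided. The instruction turns that impression into a routine tabulation.

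**The case against.** The strongest reply is that the open-label design already carries nearly all of this bias, and that deleting a few words leaves it in place. Much of that stands: it is why the added bias is called modest. It does not justify keeping a tabulation that nobody needs.

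A second reply is that the sentence looks like template text, since dose level has no meaning in this trial. That is plausible, but the sentence governs conduct as written, and being template text is a reason to correct it.

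A third is that outcomes overlap with tolerability. Section 10.1 lists application-site pain for crisaborole, and burning, stinging, soreness or pruritus for tacrolimus. This is fair. By-arm adverse-event review should continue, and it will reveal some differences between arms whatever else is withheld.

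Two stronger readings are tempting.
- A reader might infer that the reviewers are the same people who enrol, score and treat. The documents use several labels (research staff, study personnel, treating dermatologist, investigator) and the names are removed. Overlap is likely, but only the investigator's double role as reviewer and withdrawer is explicit.
- A reader might infer that section 9.3 contradicts section 11.3, which relies on "monthly data and procedural reviews by the Clinical Monitor and Investigator in consultation with study personnel". The documents do not show this. Section 9.3 describes the staff review as an additional one, continuous and monthly reviews can coexist, and section 11.3 opens with redacted text that may bear on who reviews.

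**Conclusion.** The concern holds in a limited form. The plan instructs trial staff to look continuously at outcome data by arm, and no planned decision uses what they see. In an open-label trial with discretionary withdrawal, replacement and flare management, that is a modest and avoidable addition to the bias that comes from knowing individual assignments. The documents show the opening, not that anyone would act on it.

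The size cannot be computed. A reader might want to express it as a shift in an arm's mean after poor responders are replaced. That would need the number of such children and how far they fall below the mean, neither of which is given. It would also have to assume that a replaced child's data are discarded, whereas section 11.1 counts any child who completes the week-6 assessment as evaluable. Nor can an inflated type I error rate be claimed, since no test is planned at these reviews.

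The conclusion assumes that responses means EASI, ISGA, %BSA or PRO data, and that the redacted text contains no restriction on who sees them by arm.

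**What to change.** In the research-staff paragraph of section 9.3, delete responses from the list of review items and delete the reference to dose level. Add a sentence there or in section 12: no aggregate by-arm summary of PRO, EASI, ISGA or %BSA data is produced for study staff before the last week-12 visit and database lock.

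Keep by-arm review of adverse events, including application-site pain, burning and pruritus reported as adverse events. If the Data Safety Monitoring Committee requires a by-arm outcome summary, it should go to that committee only. Because section 9.3 now has the Investigator prepare the summaries, the text should also say that someone outside day-to-day conduct prepares that one.

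The cost is a few sentences and an understanding about which reports are run. Staff lose an informal running view of outcomes. The change does not blind them to any child's assignment or course, and the plan should not suggest that it does.
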